A screening log will be maintained by research coordinators of all patients who were considered for enrollment and their demographics, clinical characteristics and the reason for their exclusion.

Sample Size

Our primary outcome is the CATH rate at 3 months. Based on our previous analyses from our IRB 2016-157 study (the FFR-ACP study), the SOC arm had a 89.5% CATH rate in the 71-99% stenosis group and 58.3% in the 51-70% stenosis group. With the 51-70% stenosis group having twice as many patients as the 71-99% group, we anticipate 68.7% of CATHs in all SOC controls. In our previous CT-FFR negative patients, there were 65.6% CATHs in the 71-99% stenosis group and 21.3% in the 51-70% stenosis group. Again with a 2 to 1 ratio, we anticipate an overall CATH rate of 36.1% in the FFR patients. Since these are estimates for the FFR group, we calculated several possibilities. All have 90% power with a significance level of 0.05%.

We determined a sample size of 87 patients per arm are needed to detect this difference. We intend to randomize 100 patients per arm to adjust for any lost to follow-up. We used PASS 15 Power Analysis and Sample Size Software (2017). NCSS, LLC. Kaysville, Utah, USA, ncss.com/software/pass.

Numeric Results for Testing Two Proportions using the Z-Test with Unpooled Variance

H0: P1 - P2 = 0. H1: P1 - P2 = D1 ≠ 0.

Target	Actual						
Diff							
Power	Power*	N1	N2	N	P1	P2	D1
Alpha							
0.90	0.90148	44	44	88	0.6870	0.3600	0.3270
0.0500							
0.90	0.90458	59	59	118	0.6870	0.4000	0.2870
0.0500							

0.90	0.90155	87	87	174	0.6870	0.4500	0.2370
0.0500							

* Power was computed using the normal approximation method.

Randomization

We intend to include 200 patients (100 per arm). Patients will be randomized in a 1:1 ratio to Standard of Care (SOC) or CT-FFR-guided management, in alternating block design to ensure equal groups periodically. The order of randomization will be generated using SAS for Windows 9.3, Cary, NC. Randomization envelopes will be generated by a Beaumont Research Biostatistician and will be opened in sequential order. Once the patient has met all the inclusion criteria, none of the exclusion criteria and has signed the informed consent, the next envelope will be opened which will contain a slip indicating the patients assigned study number and to which arm they are being randomized.

SOC Group Management

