Attending physicians will dictate SOC management according to their own clinical judgment. This could include discharge without further testing, EKG-only stress testing, stress echocardiography, stress myocardial perfusion imaging, direct admission and further noninvasive testing or CATH. In addition to standard testing, a blinded CT-FFR will be obtained for post hoc analysis, but it will not be used for patient management. Image data from our CT workstation will be sent directly to HeartFlow, Inc. over a secure research transfer node.

If attending physicians decide that SOC Group patients should undergo CATH, the protocol will specify an invasive fractional flow reserve will be performed on all lesions over 30% stenosis severity, to confirm the presence or absence of flow-limiting stenosis. This may be waived without protocol deviation if deemed unsafe by the severity of stenosis or due to clinical circumstances, as documented in a completed Physician Study Questionnaire.

CT-FFR-Guided Group Management

Patients in this group will be triaged using CT-FFR. Image data from our CT workstation will be sent directly to HeartFlow, Inc. over a secure Priority (STAT) transfer node. Interpreting physician will categorize CT-FFR results as follows:

1. CT-FFR >0.80. All CT-FFR segmental values are >0.80, with no indication of flow limiting ischemia. A non-binding recommendation that the patient undergo an initial trial of medical therapy will be made by the interpreting co-investigator. Attending physicians will be asked to complete a study Physician Questionnaire to determine whether they followed this recommendation or not, and if not, why not.
2. CT-FFR 0.70-0.80. These will be reported as values in the abnormal range without specific recommendations about whether CATH should be performed. Attending physicians will decide triage in consideration with other clinical data. Attending physicians will be asked to complete a study Physician Questionnaire to determine what clinical factors influenced their triage decision.

3. CT-FFR <0.70. These are abnormal values that are will be reported as high-risk. A non-binding recommendation that the patient undergo CATH will be made by the interpreting co-investigator. Attending physicians will be asked to complete a study Physician Questionnaire to determine whether they followed this recommendation or not, and if not, why not.

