If attending physicians decide that study patients should undergo CATH, the protocol will specify that CATH-FFR will be performed on all lesions over 30% stenosis severity, to confirm the presence or absence of flow-limiting stenosis prior to coronary intervention or triage to medical therapy. This may be waived without protocol deviation if deemed unsafe due to the severity of stenosis or due to other clinical circumstances, as documented on the Physician Study Questionnaire.

Clinical Follow-up

Patients will be followed at 1 month, 3 month and 1 year using a chart review and structured telephone interviews. Permission will be requested from patients for examination of outside medical records including office records and hospital records related to coronary artery disease.

Risks of the Study

Both the SOC and CT-FFR management strategies are currently used routinely at Beaumont Health, where ED patients' diagnostic strategy is selected according to the preference of their individual attending physician. There is no risk from the research study associated with CCTA testing, as patients will already have completed a clinically ordered CCTA test prior to their eligibility for the study.

Both SOC and CT-FFR Group patients will undergo CATH if indicated by the results of noninvasive evaluation by CT-FFR or SOC physicians' clinical judgment. Based on the baseline year prior to CT-FFR (Sept. 2014 – Aug. 2015), the CATH rate in SOC group patients was 58%. The CATH rate in CT-FFR patients during the previous research period (IRB #2016-157) from Sept. 2015 – Dec. 2016 was similar, at 79/147 patients, or 54%. Thus, the risk from the incidence of CATH was similar in the two groups. The study protocol does require CATH-FFR in patients undergoing CATH (unless there are no lesions >30%). There is a theoretical risk of rare (<1%) vascular injury due to the CATH-FFR catheter, however, CATH-FFR is a standard clinically recommended procedure prior to revascularization in CATH patients to insure accurate diagnosis of flow-limiting stenosis. If attending physicians believe there is a clinical reason that CATH-FFR should not be done, such as a lesion that is too severe, it may be omitted without protocol deviation, as long as the reason is documented in the Physician Study Questionnaire. The additional radiation risk added by CATH-FFR is estimated at <1 mSv, equivalent to <1 year of annual background radiation from environmental sources.

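### The planned CT-FFR arm catheterization rate is taken from patients labelled CT-FFR negative, and the 87 per arm belongs to a different contrast from the one derived in the text

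*Combined protocol and SAP*

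**What the plan says.** Under Sample Size, the primary outcome is catheterization by 3 months. The SOC rate, 68.7%, is a 2:1 blend of 58.3% (51-70% stenosis) and 89.5% (71-99%). For the other arm the text reads "In our previous CT-FFR negative patients, there were 65.6% CATHs in the 71-99% stenosis group and 21.3% in the 51-70% stenosis group", and after the same 2:1 weighting, "we anticipate an overall CATH rate of 36.1% in the FFR patients". It continues: "Since these are estimates for the FFR group, we calculated several possibilities". The table gives three scenarios against 68.7%: 36% (44 per arm), 40% (59) and 45% (87). The conclusion is "We determined a sample size of 87 patients per arm are needed to detect this difference", raised to 100 per arm for loss to follow-up.

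Under CT-FFR-Guided Group Management, the arm takes all CT-FFR results. Of values from 0.70 to 0.80 it says "These will be reported as values in the abnormal range without specific recommendations about whether CATH should be performed"; values below 0.70 carry a non-binding recommendation for catheterization.

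Under Risks of the Study, for the year before CT-FFR, "the CATH rate in SOC group patients was 58" per cent. The rate in CT-FFR patients in the earlier research period "was similar, at 79/147 patients, or 54" per cent. The section concludes: "Thus, the risk from the incidence of CATH was similar in the two groups".

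**The concern.** Three things do not fit together.

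- **Source group.** A rate described as coming from CT-FFR-negative patients stands in for a whole arm that also contains patients with abnormal results. If the label is right, the arm rate is understated.
- **Which difference.** The only difference derived in the prose is 68.7% versus 36.1%. The 87 per arm is for 68.7% versus 45%. No reason is given why a margin from 36.1% to 45% is enough.
- **Historical rates.** The risk section reports a 4-point gap (58% versus 54%) and calls the rates similar. The sample size plans on 23.7 to 32.7 points. The same registry study number is cited for the planning rates and for the 54%.

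The power for the primary outcome is at stake. If the trial ends without a significant difference, the reader needs to know whether the planned difference was a realistic expectation.

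**Working it through.** **1. Reproducing the plan's figures.**

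Blended rates: SOC (2 × 58.3 + 89.5)/3 = 68.7%; CT-FFR (2 × 21.3 + 65.6)/3 = 36.07%.

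The table uses an unpooled two-proportion z-test, two-sided alpha 0.05:

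n = (1.960 + 1.282)² × [p1(1 − p1) + p2(1 − p2)] / (p1 − p2)²

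With p1 = 0.687, n is 43.8, 58.0 and 86.5 for p2 = 0.36, 0.40 and 0.45. At the tabled 44, 59 and 87 per arm, power is 0.90148, 0.90458 and 0.90155. All three rows match. (The text prints the significance level as 0.05%; the table's 0.0500 is the value that reproduces.)

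For 68.7% versus 36.1% the same formula gives 44.07, so 45 per arm. At 87 per arm that contrast has over 99% power.

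**2. Sensitivity of power to the CT-FFR arm rate.** The planned test is Pearson's chi-square, so the pooled z-test applies. SOC is held at 68.7%, two-sided alpha 0.05.

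| CT-FFR arm rate | Power, 87 per arm | Power, 100 per arm |
|---|---|---|
| 36.1% | 99% | 99.8% |
| 45% | 89% | 93% |
| 50% | 71% | 77% |
| 54% | 51% | 57% |

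Power reaches 90% only if the arm rate is at most 44.6% (87 per arm) or 46.3% (100 per arm); with the unpooled test the limits are 45.1% and 46.6%.

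**3. If *negative* is correct.** The arm rate is (1 − s) × 36.07% + s × R, where s is the share with positive CT-FFR and R their catheterization rate. Neither is given. As a stand-in for R, the Appendix revascularization rates in positives, blended 2:1, give (2 × 68.2 + 86.4)/3 = 74.27%; the upper bound is 100%. The share at which the arm reaches 45% is

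- R = 74.27%: (0.450 − 0.3607)/(0.7427 − 0.3607) = 0.234
- R = 100%: (0.450 − 0.3607)/(1 − 0.3607) = 0.140

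For the 46.3% limit the shares are 0.268 and 0.160. So the margin is used up once roughly 14-23% of the arm is positive (16-27% at 100 per arm). This illustration assumes one positive share across both stenosis groups. Revascularization in the Appendix is cumulative, so 74% is not a strict lower bound at 3 months.

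**4. If *negative* is a wording slip.** Then 36.1% describes all CT-FFR patients above 50% stenosis, at the plan's 2:1 mix, and should fit with 79/147 = 53.74% in the 25-99% stenosis cohort. If a fraction w of that cohort had milder stenosis, their rate must be [0.5374 − (1 − w) × r]/w, where r is the rate above 50% stenosis:

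| w (assumed) | r = 36.1% | r = 45% |
|---|---|---|
| 1/3 | 89% | 71% |
| 0.40 | 80% | 67% |
| 1/2 | 71% | 62% |

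The milder patients would need a higher rate than the more severe ones. Both pairs of planning rates run the other way: 58.3% to 89.5%, and 21.3% to 65.6%.

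**5. Historical rates beside planning rates.** The risk section gives 58 − 54 = 4 points; the table plans on 23.7, 28.7 and 32.7. The 54% covers 25-99% stenosis, no stenosis range is stated for the 58%, and neither has a stated time horizon. They therefore give no direct power figure for this trial. What is missing is an explanation.

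**The case against.** The best defence is that *negative* is a slip and that the plan is already cautious. In the Appendix, the stenosis group above 70% (86.4% versus 30%, p = 0.003) is matched by 19/22 versus 3/10, which suggests 22 positives and 10 negatives. A rate of 65.6% cannot arise from 10 patients, but 21/32 gives it, and 32 = 22 + 10. So 65.6% may describe the whole severe group. This is a fair point, but the denominators are inferred, the same check does not explain the 21.3%, and step 4 shows that the slip reading has its own difficulty. That difficulty depends on the 2:1 mix: with about 73% of patients in the severe group, the same two rates would give 54% with no milder patients at all. But 2:1 is the plan's own ratio.

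Second, positives are probably concentrated in severe stenosis. If the severe positive share is assumed to be 2.5 times the intermediate one, 45% is reached at about 17-28% positive instead of 14-23%. The threshold moves a little; the conclusion does not.

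Third, the trial's exclusions could lower the rate in both arms, whereas the power table holds SOC at 68.7%. That is true, and it is a further reason to derive both rates close to the trial's eligibility.

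Fourth, the table shows openly that 87 goes with 45%, this is the most cautious of the three rows, 100 per arm are randomized, and the odds ratio will carry a confidence interval. All of this stands. It makes the mismatch over 87 mainly one of wording, and the interval will help in reading a null result. It does not show that 45% is a supported upper limit for the arm.

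**Conclusion.** The concern holds. The table is arithmetically correct, but the input behind it is either mislabelled or misapplied, and the documents cannot show which. On either reading the text needs correction: as a rate in negatives, 36.1% is not the arm rate; as a rate in all CT-FFR patients, it is hard to square with 54% in the same registry study. The statement that 87 per arm is needed for the derived difference is wrong as written, though in the cautious direction.

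The 90% power is conditional on an arm rate of about 45% or less (about 46% at 100 per arm) against 68.7%. At 50% it falls to 71% (87 per arm) or 77% (100 per arm). Those figures assume the SOC rate is right; the mixing and milder-group calculations rest on assumed shares and are illustrations. Type I error and the planned analysis are unaffected. This should be fixed.

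**What to change.** From the registry data already held:

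1. State which patients, and what denominators, the 65.6% and 21.3% come from. Correct the *CT-FFR negative* label, or combine positives and negatives using the observed positive share.
2. Derive the 3-month catheterization rate for all CT-FFR-managed patients and for SOC patients, as close as possible to this trial's eligibility, and reconcile the result with the 58% and 54% under Risks of the Study.
3. Say that 87 per arm refers to 68.7% versus 45%, and why 45% was chosen.
4. Restate power at 87 and 100 per arm for the corrected rates. The statement that all scenarios have 90% power can stay as a description of the tabled rows.

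The cost is a re-tabulation of existing data and rewording of one section. The stated power may become less favourable. No increase in sample size is requested.

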True negative case: CT-FFR negative and CATH-FFR negative

Proportion of correct CT-FFR triage = (True positive + True negative) / All CATH

SOC group:

True positive case: SOC chosen by attending physician for CATH confirmed by CATH-FFR. By definition, the clinicians' decision to CATH based on clinical evidence is considered an SOC positive case, there can be no SOC true negative cases that go to CATH.

Proportion of correct SOC triage = True positive / All CATH

2. Safety: Patients following CT-FFR-guided management will have similar MACE rates, including death, ACS and unanticipated late revascularization when compared to SOC-guided patients.

Methods

Study Population

The study population will be drawn from ED ACP who have already undergone CCTA for diagnosis, and have been found to have 50% or greater stenosis but less than 90% of at least one coronary branch. Two-hundred patients meeting entry criteria will be enrolled from a sample of ED ACP patients at Beaumont Hospital (Royal Oak). These patients will be randomized 1:1 using sealed envelopes provided by the study statistician, to either standard of care (SOC) or CT-FFR management. (See Figure 1. Study Diagram)

Inclusion Criteria

1. Emergency department or inpatients admitted through the ED with chest pain suspicious for ACS based on history and physical examination.
2. At least one biomarker (troponin) and electrocardiogram with no evidence of definite ACS.
3. A completed CCTA demonstrating $\geq 50\%$ but $< 90\%$ stenosis of at least one coronary artery branch.
4. CCTA test images with sufficient diagnostic quality for CT-FFR analysis.
5. Ability and willingness to provide informed consent.

Exclusion Criteria

- 1 Left main coronary stenosis of 50% or greater.
- 2 CCTA lesions demonstrating stenosis >90% ("subtotal"), or complex, high-risk plaque characteristics resulting in an a priori recommendation for triage to CATH by CCTA interpreting physician.
- 3 Attending physician a priori decision for CATH.
- 4 Prior coronary stent, coronary bypass or prior known myocardial infarction.
- 5 Clinical instability, such as hypotension, signs of shock, and/or unrelieved or accelerating chest pain.
- 6 Pregnancy

Obtaining Consent

Consent will be obtained by a co-investigator. Patients will have at least 20 minutes to consider whether they wish to consent.

Screening Log

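### The ambiguous "alternating block" scheme, with sequential envelopes in an open single-site trial, could make some assignments predictable before discretionary CATH exclusions are applied

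*Combined protocol and SAP*

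**What the plan says.** All places are in the combined protocol and SAP.

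- **Scheme (Randomization).** "Patients will be randomized in a 1:1 ratio to Standard of Care (SOC) or CT-FFR-guided management", "in alternating block design to ensure equal groups periodically". Also: "The order of randomization will be generated using SAS for Windows 9.3, Cary, NC". Block size, and whether it varies at random, are not given.
- **Envelopes (Study Population; Randomization).** "These patients will be randomized 1:1 using sealed envelopes provided by the study statistician". "Randomization envelopes will be generated by a Beaumont Research Biostatistician and will be opened in sequential order". The slip is seen only after eligibility is settled and the patient "has signed the informed consent, the next envelope will be opened". Opacity, who holds the envelopes and who keeps the allocation history are not stated.
- **Setting.** One hospital enrols. In the CT-FFR arm the result reaches the attending physician, with a recommendation when it is above 0.80 or below 0.70. In the SOC arm the CT-FFR is withheld from management.
- **Discretionary exclusions (Exclusion Criteria).** Exclusion 3 reads "Attending physician a priori decision for CATH", with no objective criterion. Exclusion 2 combines an objective limit (stenosis above 90%) with plaque features that lead the CCTA reader to recommend CATH in advance.
- **Roles.** A co-investigator takes consent, and a co-investigator interprets the CT-FFR.
- **Screening Log.** Coordinators record everyone considered and the reasons for exclusion. No analysis of the log is planned.
- **Primary outcome (Sample Size).** CATH rate at 3 months.

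**The concern.** Sealing an envelope hides the current slip. It does not stop someone inferring that slip from the ones already opened. A scheme known to equalise the arms periodically tells an observer which arm is due, and with a fixed or regularly alternating block size the end of each block becomes certain. In an open trial at one hospital, past assignments may be visible to the people who recruit.

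This matters more here than in most trials because two exclusions turn on someone's view that the patient should go to CATH, and CATH is the primary outcome. Both judgements precede the opening of the envelope. If such a judgement were applied more readily when one arm was expected next, the arms would differ at entry in their likelihood of CATH. The planned primary test is an unadjusted Pearson chi-square, which would carry that difference into the result.

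**Working it through.** **1. Scale of the design.** The Sample Size section gives P1 = 0.687, P2 = 0.45, two-sided alpha 0.05 (table), 90% power and an unpooled Z-test.

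n = [P1(1−P1) + P2(1−P2)] × (1.960 + 1.282)² / (P1−P2)²
= (0.2150 + 0.2475) × 10.51 / 0.237² = 86.5, so 87 per arm, as stated. The point below does not alter this number. The reference effect is 23.7 points, with 200 patients planned.

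**2. How predictable is the next assignment?** Block sizes are assumed, since none is given. For a 1:1 permuted block of known size 2m, the expected number of assignments already determined at the end of the block is 2m/(m+1), so the certain share is 1/(m+1). The second column is the share guessed correctly by always naming the under-represented arm (chance is 50%).

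| Scheme | Certain | Guessed correctly |
|---|---|---|
| Literal alternation | 100% | 100% |
| Blocks of 2 | 1/2 = 50% (100 of 200) | 75% |
| Blocks of 4 | 1/3 = 33% (67 of 200) | 70.8% |
| Blocks of 6 | 1/4 = 25% (50 of 200) | 68.3% |
| Alternating 4 and 6 | (4×1/3 + 6×1/4)/10 = 28% (57 of 200) | 69.3% |
| Random 4, 6, 8 (simulated) | about 2%, even if the set of sizes is known | 68% |

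The certain shares for fixed or alternating blocks apply only to someone who knows or has inferred the block size and has followed the sequence.

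**3. What could that do to the primary comparison?** Assume no true effect and a CATH rate p in both arms. Take p as 0.687 (the plan's SOC rate) or 0.54 (79/147, Risks of the Study). Assume also that a share q of CATH-bound patients is excluded whenever CT-FFR is guessed to be next; q is not in the documents. The CATH rate among patients enrolled at those moments is p(1−q)/(1−pq). With correct-guess rate g, the expected bias is

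[p − p(1−q)/(1−pq)] × (2g − 1).

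Example: p = 0.54, q = 0.30. The rate falls to 0.378/0.838 = 0.451, a drop of 8.9 points. With blocks of 4, 2g − 1 = 0.417 and the bias is 3.7 points.

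| p | q | Bias, blocks of 4 | Bias, random 4/6/8 | Bias, alternation |
|---|---|---|---|---|
| 0.54 | 10% | 1.1 | 0.9 | 2.6 |
| 0.54 | 20% | 2.3 | 2.0 | 5.6 |
| 0.54 | 30% | 3.7 | 3.2 | 8.9 |
| 0.687 | 10% | 1.0 | 0.8 | 2.3 |
| 0.687 | 20% | 2.1 | 1.8 | 5.0 |
| 0.687 | 30% | 3.4 | 2.9 | 8.1 |

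Bias is in percentage points, in favour of CT-FFR under this assumed direction of steering; opposite steering would reverse the sign. Simulation of the chi-square test (200 patients, 6,000 runs per setting) gives the same biases to within rounding and simulation error. Its type I error is about 0.05 to 0.09 for the permuted-block schemes and 0.07 to 0.26 for literal alternation, against 0.05 to 0.06 with no steering.

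**The case against.** The best case for the plan has four parts.

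- **The phrase need not describe a weak scheme.** It may mean permuted blocks of alternating size, and generating the order in SAS argues against plain ABAB. This stands: the text does not establish that assignments are guessable. It equally does not rule out the regular schemes, and clarifying it costs nothing.
- **The roles are partly separate.** The biostatistician prepares envelopes, coordinators keep the log, a co-investigator takes consent, the attending physician decides exclusion 3 and the CCTA reader contributes to exclusion 2. A reader might infer that everyone enrolling knows all earlier assignments. The documents do not say so. Exclusion 3 can bias enrolment only if the attending physician, or someone who influences that decision, follows the sequence.
- **There are safeguards.** Sealing, opening after consent and the screening log are real. They prevent early reading of a slip and leave a record, but they do not block inference from past slips.
- **Imbalance could be seen and partly corrected.** A reader might conclude that no analysis could repair selective enrolment. That is too strong: stenosis category is recorded, and a subset analysis by intermediate and severe stenosis is pre-specified, so imbalance in category could be adjusted for. Selection on unrecorded judgement could not.

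A larger effect is also tempting. With blocks of 4, suppose half of the certain slots were steered between severe and intermediate patients: 1/3 × 1/2 × (0.895 − 0.583) = 5.2 points. The documents do not support that figure. The one-half is arbitrary. Exclusions can remove a patient but cannot choose who fills a slot. The 89.5% comes from a 71-99% stenosis group, whereas this trial enrols below 90% and excludes patients with an a priori CATH decision.

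**Conclusion.** The point holds as an avoidable risk from an undefined allocation scheme. It is not evidence that bias would occur. If past assignments are tracked and a fixed or regular block size is known or inferred, 25% to 50% of assignments are certain for blocks of 6 down to 2, and all are certain under literal alternation. Combined with discretionary CATH exclusions made before allocation, that leaves room for selection on the primary outcome.

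Under permuted blocks and an assumed 10% to 30% selective exclusion, the effect is modest: about 1 to 4 points, at most about a sixth of the 23.7-point design difference (3.7/23.7 = 0.16). It would be larger under literal alternation, which is the less likely reading. The block sizes, the exclusion share and the direction of steering are all assumptions. Sample size and power calculations are unaffected. This is a cheap improvement, not a threat to the trial's validity as it stands.

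**What to change.** 1. In Randomization, replace the alternating block wording with computer-generated, randomly permuted blocks of randomly varying size (for example 4, 6 and 8). Only the biostatistician holds the sizes, and the protocol does not state them.
2. State that the sealed envelopes are opaque. Keep them, and the allocation history, with existing staff who neither recruit nor judge eligibility.
3. In the existing screening log, time-stamp the attending physician's a priori CATH decision and the CCTA reader's a priori CATH recommendation before allocation is requested.

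Step 1 cuts certain assignments to about 2%. It does little against guessing from the running imbalance, which stays near 68% correct; the bias table shows only a small drop for a recruiter who acts on best guesses. Steps 2 and 3 are therefore needed as well: the first limits access to the history, and the second makes selective exclusion detectable.

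The cost is a revised SAS list, a few sentences and one log field, with no change in sample size. The downside is a slightly larger temporary imbalance between arms.
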